	
implantation.
 
EC26. Subject has severe incapacitating dementia.
 
Additional exclusion criteria apply for subjects considered for enrollment in the CT Imaging substudy of the U.S. Continued Access Study as listed below.
 
AEC1. Subject has eGFR <30 mL/min (chronic kidney disease stage IV or stage V).
 
AEC2. Subject has atrial fibrillation that cannot be rate controlled to ventricular response rate < 60 bpm.
 
AEC3. Subject is expected to undergo chronic anticoagulation therapy after the TAVR procedure.
 
Note: Subjects treated with short-term anticoagulation post-procedure can be included in the imaging substudy; in these subjects the 30-day imaging will be performed 30 days after discontinuation of anticoagulation.

Statistical Methods	
Analysis Sets	
Analysis sets for the randomized cohort are listed below.
 
As-Treated: This population includes all subjects who sign an Informed Consent Form, are enrolled in the trial, are randomized, and received a study device, but is based on the treatment actually received.
 
Intention-To-Treat (ITT): This population includes all subjects who sign an Informed Consent Form, are enrolled in the trial, and are randomized, whether or not an assigned study device is implanted.
 
Implanted: This population includes all subjects who sign an Informed Consent Form, are enrolled in the trial, and are implanted with the assigned, randomized study device.
 
For all randomized cohort analysis sets, if a subject receives 2 valves, the subject is assigned to the group corresponding to the first valve received.
 
Among the roll-in (initial cohort with the 23, 25 and 27 mm Lotus), Lotus 21 mm Nested Registry, LOTUS Edge Nested Registry, roll-in with the 29 mm LOTUS Edge, LOTUS Edge 29 mm Nested Registry, and U.S. Continued Access cohorts, for ITT analyses all subjects who sign an Informed Consent Form and are enrolled in the study will be included in the analysis sample, regardless of whether the study device was implanted. The As-Treated population is the same as the Implanted population for these cohorts and includes all subjects who sign an Informed Consent Form

REPRISE III: REpositionable Percutaneous Replacement of Stenotic Aortic Valve through Implantation of Lotus™ Valve System – Randomized Clinical Evaluation	
	and are implanted with the Lotus Valve.

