Success Criteria for the Primary Effectiveness Endpoint – Non-Inferiority	If the P value from the Farrington-Manning standardized test is <0.025, the rate of the primary effectiveness endpoint for the Lotus Valve will be concluded to be non-inferior to the CoreValve rate. This corresponds to the one-sided upper 97.5% confidence bound on the difference between treatment groups (Lotus Valve minus CoreValve) for the observed rate of the primary effectiveness endpoint being less than delta.

REPRISE III: REpositionable Percutaneous Replacement of Stenotic Aortic Valve through Implantation of Lotus™ Valve System – Randomized Clinical Evaluation	
Statistical Test Method for the Primary Effectiveness Endpoint – Superiority	
A chi-square test will be used to test the two-sided hypothesis of superiority of the Lotus Valve versus CoreValve:
 $H_0: P_{E\_Lotus} = P_{E\_Control}$ $H_1: P_{E\_Lotus} \neq P_{E\_Control}$ 
where <math>P_{E\_Lotus}</math> and <math>P_{E\_Control}</math> correspond to the rates of the primary effectiveness endpoint for the Lotus Valve group (test) and the CoreValve group (control), respectively.
 
The primary analysis set for superiority test of the primary effectiveness endpoint is the ITT analysis set. This endpoint will also be analyzed for the as-treated and implanted analysis sets.

Sample Size Parameters for the Primary Effectiveness Endpoint – Superiority	
 
• Expected Lotus Valve (test) rate <math>P_{E\_Lotus} = 22\%</math>
 
• Expected CoreValve (control) rate <math>P_{E\_Control} = 32\%</math>
 
• Test significance level (<math>\alpha</math>) = 0.05 (2-sided)
 
• Test : Control ratio = 2:1
 
• Power (<math>1-\beta</math>) = 80%
 
• Total number of evaluable subjects = 684
 
• Expected rate of attrition = 10%
 
• Given enrollment of 912 subjects (608 Lotus Valve, 304 CoreValve) and 10% attrition, there is approximately 86% power to show superiority with the given expected rates
 

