Success Criteria for the Primary Effectiveness Endpoint – Superiority	
If the <math>P</math> value from the chi-square test is <math><0.05</math> and the rate of the Lotus Valve group is less than the rate of the CoreValve group, the rate of the primary effectiveness endpoint for the Lotus Valve will be concluded to be superior to the CoreValve rate. This corresponds to the two-sided upper 95% confidence bound on the difference between treatment groups (Lotus Valve minus CoreValve) for the observed rate of the primary effectiveness endpoint being less than zero.

Secondary Endpoint Statistical Hypothesis	
The secondary endpoint of moderate or greater paravalvular aortic regurgitation rate at 1 year (based on core lab assessment) for the Lotus Valve group is superior to that for the CoreValve group.

REPRISE III: REpositionable Percutaneous Replacement of Stenotic Aortic Valve through Implantation of Lotus™ Valve System – Randomized Clinical Evaluation	
Statistical Test Method for the Secondary Endpoint	
A chi-square test will be used to test the two-sided hypothesis of superiority:
 $H_0: P_{AR\_Lotus} = P_{AR\_Control}$ $H_1: P_{AR\_Lotus} \neq P_{AR\_Control}$ 
where <math>P_{AR\_Lotus}</math> and <math>P_{AR\_Control}</math> correspond to the moderate or greater paravalvular aortic regurgitation rates at 1 year for the Lotus Valve group (test) and the CoreValve group (control), respectively.
 
The primary analysis set for the secondary endpoint is the ITT analysis set. This endpoint will also be analyzed for the as-treated and implanted analysis sets.

Sample Size Parameters for the Secondary Endpoint	
 
• Expected Lotus Valve (test) rate <math>P_{AR\_Lotus} = 1.1\%</math>
 
• Expected CoreValve (control) rate <math>P_{AR\_Control} = 5.3\%</math>
 
• Test significance level (<math>\alpha</math>) = 0.05 (2-sided)
 
• Test : Control ratio = 2:1
 
• Expected rate of attrition = 25%
 
• Given enrollment of 912 subjects (608 Lotus Valve, 304 CoreValve) and 25% attrition, there is approximately 86% power to show superiority with the given expected rates
 

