## 7. Endpoints

Outcomes will be assessed on an intention-to-treat (ITT) basis, an implanted basis, and an as-treated basis. The ITT analysis population of the randomized cohort includes subjects who sign an Informed Consent Form (see Section 0), are enrolled in the trial (see Section 10.1 for point of enrollment), and are randomized, whether or not an assigned study device is implanted. The implanted analysis population includes ITT subjects who are implanted with an assigned, randomized study device. The as-treated population includes subjects who sign an Informed Consent Form, are enrolled in the trial, are randomized, and received a study device, with the analysis based on the treatment actually received. For all analysis sets, if a subject receives 2 valves, the subject is assigned to the group corresponding to the first valve received. Among the roll-in (initial cohort with 23 mm, 25 mm, and 27 mm Lotus Valve System and subsequent cohort with 29 mm LOTUS Edge Valve System), Lotus 21 mm Nested Registry, LOTUS Edge Nested Registry, LOTUS Edge 29 mm Nested Registry, and U.S. Continued Access Study cohorts, for ITT analyses, all subjects who sign the IRB/IEC-approved study ICF and are enrolled in the trial will be included in the analysis sample, regardless of whether the study device was implanted. For these cohorts, the as-treated population includes all subjects implanted with the Lotus/LOTUS Edge valve. Endpoint definitions can be found in Table 26.2-1.

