### 12.2.1. Analysis Sets

The primary endpoints and additional measurements will be analyzed on an ITT, an as-treated, and an implanted basis. Among the randomized cohort, for ITT analyses, all subjects who sign the IRB/IEC-approved study ICF (see Section 11.3), are enrolled in the trial, and are randomized will be included in the analysis, whether or not an assigned study valve (Lotus Valve or CoreValve) was implanted. The as-treated population includes all subjects who sign the IRB/IEC-approved study ICF, are enrolled in the trial, and are randomized, with the analysis based on the treatment actually received (for example, if a subject is assigned to receive a test device but instead receives a control device, that subject will be considered a control subject for the as-treated analyses). For implanted analyses, ITT subjects who had the assigned, randomized study valve (Lotus Valve or CoreValve) implanted will be included in the analysis. For all analysis sets, if a subject receives 2 valves, the subject is assigned to the group corresponding to the first valve received. Among the roll-in (with the 23 mm, 25 mm, or 27 mm Lotus Valve), Lotus 21 mm Nested Registry, LOTUS Edge Nested Registry, roll-in with the 29 mm LOTUS Edge Valve, LOTUS Edge 29 mm Nested Registry, and U.S. Continued Access Study cohorts, for ITT analyses, all subjects who sign the IRB/IEC-approved study ICF and are enrolled in the trial will be included in the analysis sample, regardless of whether the study device was implanted. For these cohorts, the as-treated population includes all subjects implanted with the Lotus Valve. The as-treated and implanted analysis sets are the same for these cohorts.

For the randomized cohort, the primary safety endpoint, primary effectiveness endpoint (both hypotheses), and the secondary endpoint will all be analyzed for the ITT, as-treated, and implanted analysis sets. The primary analysis for the primary hypothesis of the primary effectiveness endpoint and the primary safety endpoint will be based on the implanted analysis set. The primary analysis set for the secondary hypothesis of the primary effectiveness endpoint and the secondary endpoint will be based on the ITT analysis set.

After 1 year, all analyses will be based on the safety analysis set. All subjects who sign the written ICF, are enrolled in the study, and have a study device implanted regardless of the device and treatment assignment will be included in the safety analysis set.

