HOSTILE CHEST	
Any of the following or other reasons that make redo operation through sternotomy or right anterior thoracotomy prohibitively hazardous:
 
 
● Abnormal chest wall anatomy due to severe kyphoscoliosis or other skeletal abnormalities (including thoracoplasty, Potts' disease)
 
● Complications from prior surgery
 
● Evidence of severe radiation damage (e.g. skin burns, bone destruction, muscle loss, lung fibrosis or esophageal stricture)
 
● History of multiple recurrent pleural effusions causing internal adhesions
 

IMPLANTED ANALYSIS SET	
This population includes all subjects who sign an Informed Consent Form, are enrolled in the trial, and are implanted with the assigned, randomized study device.
 
Note 1: If a subject receives 2 valves, the subject is assigned to the group corresponding to the first valve received.

INTENT TO TREAT (ITT) ANALYSIS SET	
This population includes all subjects who sign an Informed Consent Form, are enrolled in the trial, and are randomized, whether or not an assigned study device is implanted. Subjects in the ITT population will be followed with their ITT cohort.
 
Note 1: If a subject receives 2 valves, the subject is assigned to the group

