**Table 26.2-1: Definitions**

Term	Definition
	corresponding to the first valve received.
INTERNAL MAMMARY ARTERY OR OTHER CRITICAL CONDUIT(S) CROSSING MIDLINE AND/OR ADHERENT TO POSTERIOR TABLE OF STERNUM	
A patent IMA graft that is adherent to the sternum such that injuring it during reoperation is likely. A patient may be considered extreme risk if any of the following are present:
 
 
• The conduit(s) are radiographically indistinguishable from the posterior table of the sternum.
 
• The conduit(s) are radiographically distinguishable from the posterior table of the sternum but lie within 2-3mm of the posterior table.
 

INTRACRANIAL HEMORRHAGE	Collection of blood between the brain and skull; subcategorized as epidural, subdural, and subarachnoid bleeds.
LEFT BUNDLE BRANCH BLOCK (LBBB)	
The appearance of typical complete LBBB in the three KEY leads (I, V1, and V6) with the following diagnostic criteria [see Figure below].
 
 
• The heart rhythm must be supraventricular in origin
 
• QRS widening to at least 0.12 sec
 
• An upright (monophasic) QRS complex in leads I and V6; the QRS may be notched, but there should not be any q wave in either lead I or lead V6.
 
• A predominantly negative QRS complex in lead V1; there may or may not be an initial small r wave in lead V1, that is, lead V1 may show either a QS or RS complex.
 
 
LIVER DISEASE (SEVERE) /CIRRHOSIS	
Any of the following:
 
 
• Child-Pugh class C
 
• MELD score <math>\geq 10</math>
 
• Portal-caval, spleno-renal, or transjugular intrahepatic portal shunt
 
• Biopsy proven cirrhosis with portal hypertension or hepatocellular dysfunction
 

MITRAL VALVE APPARATUS DAMAGE	Angiographic or echocardiographic evidence of a new damage to the mitral valve apparatus (chordae papillary muscle, or leaflet) during or after the TAVR procedure.
MODIFIED DEVICE SUCCESS	Absence of mortality with the originally implanted transcatheter valve in the proper anatomical location, no additional aortic valve procedures, and with the intended performance of the prosthetic valve (either a mean aortic valve gradient $< 20$ mm Hg or a peak velocity $< 3$ m/sec with no moderate or severe prosthetic valve aortic regurgitation)

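### The first-valve rule is written for every randomised analysis set, including the ITT set behind both superiority tests: wrong as worded for ITT, though probably very small in effect

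*Combined protocol and SAP*

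**What the plan says.** The Synopsis lists the as-treated, ITT and implanted sets for the randomised cohort and then adds: "For all randomized cohort analysis sets, if a subject receives 2 valves, the subject is assigned to the group corresponding to the first valve received". Section 7 has the same rule: "For all analysis sets, if a subject receives 2 valves, the subject is assigned to the group corresponding to the first valve received". Section 12.2.1 repeats it after defining the three sets. None of the three places exempts ITT.

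Table 26.2-1 puts the rule inside the ITT definition. That entry says "Subjects in the ITT population will be followed with their ITT cohort", and its Note 1 then assigns a two-valve subject to the group "corresponding to the first valve received".

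ITT is the primary set for both superiority tests. For effectiveness the Synopsis says "The primary analysis set for superiority test of the primary effectiveness endpoint is the ITT analysis set"; for the secondary endpoint, "The primary analysis set for the secondary endpoint is the ITT analysis set". Section 12.2.1 confirms both: "The primary analysis set for the secondary hypothesis of the primary effectiveness endpoint and the secondary endpoint will be based on the ITT analysis set".

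Regrouping by treatment received is otherwise described only for the as-treated set. Section 12.2.1 takes a subject assigned to the test device who receives the control device instead, and says "that subject will be considered a control subject for the as-treated analyses". The as-treated entry in Table 26.2-1 gives the same example.

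**The concern.** An ITT comparison rests on groups fixed by randomisation. Which valve went in first, and whether a second followed, are known only afterwards. Under the written rule these events decide the arm for some subjects in the analysis that carries the superiority claims.

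The rule also treats like cases differently. A subject who receives one valve, not of the assigned type, meets no ITT regrouping rule and so stays in the randomised arm. A subject with the same crossover who then receives a second valve is moved.

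Both superiority tests are confirmatory. Under the hierarchy in Section 12.1, PVR superiority must be shown before effectiveness superiority is tested, so a change in the first result also decides whether the second test is run. The two non-inferiority tests use the implanted set as primary and are not part of this point.

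**Working it through.** **1. What the text does to each type of subject in the ITT set**

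| Valves received | Group under the written rule | Same as randomised arm? |
|---|---|---|
| One, as assigned | No regrouping rule applies | Yes |
| One, not as assigned | No regrouping rule applies in ITT (as-treated only) | Yes, on the ordinary meaning of ITT |
| Two, first as assigned | First valve | Yes |
| Two, first not as assigned | First valve | **No** |

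Only the last row is affected. The protocol foresees both ingredients: off-assignment implantation in the as-treated example, and second valves through the TAV-in-TAV entry in Table 26.2-1. It gives no frequency for the combination.

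**2. The plan's own figures for the two ITT tests**

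Inputs (Sections 12.1.2.2.2 and 12.1.3.2): 608 Lotus and 304 CoreValve, two-sided alpha 0.05. Effectiveness is 22% vs 32% with 10% attrition; PVR is 1.1% vs 5.3% with 25% attrition.

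Power = Φ[(|p1 − p2| − 1.96·SE0)/SE1], with SE0 from the pooled rate and SE1 from the separate rates.

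- Effectiveness: CoreValve n = 304 × 0.90 = 273.6, pooled rate 0.2533, SE0 = 0.0322, SE1 = 0.0333. Power = Φ[(0.10 − 0.0631)/0.0333] = 86.6% (stated: about 86%).
- At 684 evaluable subjects (228 CoreValve), effectiveness power is 80.1% (stated: 80%).
- PVR: CoreValve n = 304 × 0.75 = 228, pooled rate 0.025, SE0 = 0.01266, SE1 = 0.01562. Power = Φ[(0.042 − 0.0248)/0.01562] = 86.4% (stated: about 86%).

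These figures reproduce. The correction changes none of them.

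**3. Sensitivity at the planned counts**

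The test is the Pearson chi-square without continuity correction. A moved subject takes both the event and the place in the denominator to the other arm. Evaluable numbers are 456 and 228 for PVR, and 547 and 274 for the composite.

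Planned PVR events are 1.1% × 456 ≈ 5 and 5.3% × 228 ≈ 12. The pooled rate is 17/684 = 0.0249, the difference 0.0417 and its standard error 0.0126, so z = 3.30 and P = 0.00097. Moving k CoreValve events to Lotus gives:

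| k | Lotus | CoreValve | P |
|---|---|---|---|
| 0 | 5/456 | 12/228 | 0.00097 |
| 1 | 6/457 | 11/227 | 0.0052 |
| 2 | 7/458 | 10/226 | 0.022 |
| 3 | 8/459 | 9/225 | 0.075 |

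Planned composite events are 22% × 547 ≈ 120 and 32% × 274 ≈ 88, P = 0.0016. Nine moves give 129/556 vs 79/265, P = 0.042; ten give 130/557 vs 78/264, P = 0.056.

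**4. Sensitivity in borderline tables**

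These counts are assumed and were chosen to sit near 0.05. They are illustrations, not estimates of the rule's effect. Counts are Lotus vs CoreValve.

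| One subject moved | Before | P | After | P |
|---|---|---|---|---|
| PVR event, Lotus to CoreValve | 11/456 vs 12/228 | 0.051 | 10/455 vs 13/229 | 0.017 |
| PVR event, CoreValve to Lotus | 5/456 vs 9/228 | 0.013 | 6/457 vs 8/227 | 0.054 |
| Composite event, Lotus to CoreValve | 141/547 vs 88/274 | 0.056 | 140/546 vs 89/275 | 0.043 |
| Composite event, CoreValve to Lotus | 140/547 vs 88/274 | 0.049 | 141/548 vs 87/273 | 0.064 |
| PVR event-free, Lotus to CoreValve | 7/456 vs 9/228 | 0.049 | 7/455 vs 9/229 | 0.051 |

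In the one borderline table checked, moving an event-free subject shifts P by about 0.002.

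**The case against.** The strongest reply is that the documents are inconsistent, not one-directional. Only the as-treated set is described as based on treatment received. ITT covers everyone randomised, implanted or not, and those subjects are said to stay with their ITT cohort. An analyst could reasonably take that to mean the randomised arm. Moreover, Sections 12.1.2.1.2 and 12.1.3.1 send both superiority tests to the Statistical Analysis Plan, and Section 12.2 says all analyses follow it. That plan could settle the matter.

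This limits what can be claimed. A reader might infer that such subjects will be analysed in the wrong arm. The documents do not support that: they show what the protocol's wording directs, not what the analysis will do. The reply does not remove the fault, however. The sentence about the ITT cohort concerns follow-up, and Note 1 comes directly after it. A specific written rule, repeated in four places including the ITT definition itself, should not depend on an analyst setting it aside.

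The second reply is that the effect is close to nil. In the more readily foreseen two-valve case, a second valve placed after the assigned one, the rule returns the randomised arm. Both endpoints are also analysed in the as-treated and implanted sets. This stands, and it is why the point is rated minor in effect.

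**Conclusion.** The rule is wrong for ITT as worded. It lets the first valve received decide the arm in an analysis labelled ITT, and it conflicts with the protocol's own placing of such regrouping in the as-treated set. This is a stated rule that needs correcting, not a missing detail.

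The expected effect is minor. Only subjects with two valves, the first not of the assigned type, are affected; their number is not given and is probably very small. Results at the planned counts are robust.

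A reader might infer from the borderline tables that the superiority conclusions are fragile or that the rule favours Lotus. Neither follows. Those tables were chosen to sit near 0.05 and each moves one subject by assumption. The rule is worded identically for both arms, and a move can push P either way.

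The conclusion assumes that the separate Statistical Analysis Plan does not already place ITT subjects in the randomised arm. Its text was not in the material reviewed.

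**What to change.** Before analysis:

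- In the Synopsis, Section 7, Section 12.2.1 and Table 26.2-1, state that in ITT analyses every subject is analysed in the arm to which the subject was randomised, whatever valve or number of valves is received.
- In the same places, limit the first-valve rule to the as-treated and implanted sets, where it can stay as it is.
- Delete Note 1 from the ITT entry in Table 26.2-1.
- Check that the Statistical Analysis Plan says the same.

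The cost is wording only. No new data are needed, the as-treated and implanted sets keep their rule, and the 912 subjects, 684 evaluable subjects and power of about 86% are unchanged. Settling the wording now also avoids a dispute about a subject's arm once results are known.

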## 4. Introduction

This protocol specifies procedures and contains information relevant to the clinical evaluation of the Lotus™ Valve System and LOTUS Edge™ Valve System, transfemoral aortic valve replacement devices designed and manufactured by Boston Scientific Structural Heart a Division of Boston Scientific Corporation (BSC). The Lotus Valve System and LOTUS Edge™ Valve System both consist of a pre-loaded, stent-mounted tissue valve prosthesis and catheter delivery system designed to enable predictable and precise placement of the valve during transcatheter aortic valve replacement (TAVR). Early leaflet function during valve deployment and the presence of a radiopaque tantalum marker on the braided frame facilitate optimal initial positioning of the valve. If needed, the valve may be partially or fully resheathed for repositioning prior to final release or can be fully retrieved if during the procedure the decision is made not to implant. The valve also has a polycarbonate-based urethane outer seal (Adaptive Seal™) designed to minimize paravalvular leakage. Additionally, the LOTUS Edge valve has tantalum (radiopaque) markers on the valve locking assembly (*i.e.*, buckle and post-top components) to aid in visualization of locking during the procedure and a catheter delivery system designed for improved deliverability. More detailed description of the devices can be found in Section 5 and in the Investigator Brochure. With the Lotus Valve System as the test device, study subjects will be entered into the roll-in cohort, randomized (test versus control) cohort, a single-arm, nested registry cohort of subjects who receive the 21 mm Lotus Valve (Lotus 21 mm Nested Registry), or the U.S. Continued Access Study cohort (which will include a 4D computed tomography [CT] substudy cohort). Study subjects will also be enrolled in a single-arm, nested registry with the 23 mm, 25 mm, and 27 mm LOTUS Edge Valve System (LOTUS Edge Nested Registry). Additionally, study subjects will be entered into a roll-in cohort and a single-arm, nested registry cohort of subjects who receive the 29 mm LOTUS Edge Valve System (LOTUS Edge 29 mm Nested Registry). Additional information on study design can be found in Section 8.

